**Formulation and Stability:**

Caspofungin is available as a lyophilized white to off-white powder/cake as a single-use vial in two vial sizes (50 mg and 70 mg). Each vials contains an intentional overfill. The 50 mg vials contain 54.6 mg and the 70 mg vial contains 75.6mg. The 50mg vials also contain 39 mg of sucrose and 26 mg of mannitol. The 70 mg vials also contain 54 mg of sucrose and 36 mg of mannitol. The pH is adjusted during manufacturing with glacial acetic acid and sodium hydroxide. The lyophilized powder vials should be stored refrigerated at 2° to 8°C (36 to 46°F).

**Guidelines for Administration:** See Treatment and Dose Modification sections of the protocol.

**Preparation instructions in this monograph apply only to the Merck USA product as supplied for this study.**

Prior to reconstitution, equilibrate the refrigerated vial to room temperature. Aseptically add 10.8 mL of 0.9% Sodium Chloride Injection, Sterile Water for Injection, Bacteriostatic Water for Injection with methylparaben and propylparaben, or Bacteriostatic Water for Injection with 0.9% benzyl alcohol to the

vial. Use diluents **without** benzyl alcohol for neonates and infants < 2 years of age or patients with hypersensitivity to benzyl alcohol.

The concentration of the reconstituted solution depends on the vial size and is listed in the table below:

CANCIDAS vial*	Total Drug Content (including overfill)	Reconstitution Volume to be added*	Resulting Concentration following Reconstitution**
50 mg	54.6 mg	10.8 mL	5 mg/mL
70 mg	75.6 mg	10.8 mL	7 mg/mL

\*Preparation instructions apply only to the Merck USA product as provided in this study.

\*\*Note different concentrations following reconstitution of the product in the vial.

The white to off-white cake will dissolve completely. Mix gently until a clear solution is obtained. Visually inspect the reconstituted solution for particulate matter or discoloration during reconstitution and prior to infusion. Do not use hazy, precipitated, or discolored solutions. The reconstituted solution may be stored for up to 1 hour at  $\leq 25^{\circ}\text{C}$  ( $\leq 77^{\circ}\text{F}$ ). Since caspofungin vials are for single use only; the remaining solution should be discarded.

Dilute the appropriate volume of reconstituted caspofungin in 0.9%, 0.45% or 0.225% Sodium Chloride Injection or Lactated Ringers Injection. The final concentration should not exceed 0.5 mg/mL. The stability of the diluted solution for administration is 24 hours if stored at  $\leq 25^{\circ}\text{C}$  ( $\leq 77^{\circ}\text{F}$ ) or 48 hours if stored refrigerated at 2 to 8°C (36 to 46°F). Since the infusion solution contains no preservatives and as with all parenteral drug products, aseptic technique must be used during the preparation of the infusion bag. Institution guidelines should be followed to determine the expiration time of the infusion solution. The expiration time should not exceed 24 hours at  $\leq 25^{\circ}\text{C}$  ( $\leq 77^{\circ}\text{F}$ ) and 48 hours refrigerated.

Caspofungin is administered by slow intravenous infusion over no less than 1 hour. Do not mix or co-infuse caspofungin with other medications, as there are no data available on the compatibility of caspofungin with other intravenous medications. **DO NOT USE DILUENTS CONTAINING DEXTROSE** since caspofungin is not stable in diluents containing dextrose. The infusion line should be flushed with 0.9% sodium chloride before and after drug administration.

**Supplier:** Caspofungin will be supplied by the manufacturer Merck & Company, Inc., USA. The University of Pennsylvania School of Medicine will distribute the study medication to the study sites through their Investigational Drug Service Pharmacy. Drug ordering and drug destruction information can be found on the study website. Drug receiving and accountability records should be maintained and performed according to local institutional procedures.

**If local regulations do not allow for dispensing of investigational drug supply for home use, commercial drug supply may be used for patients at home. All hospitalized patients must receive drug from investigational inventory.**

**7.0 EVALUATIONS/MATERIAL AND DATA TO BE ACCESSIONED**

Timing of protocol therapy administration, response assessment studies, and surgical interventions are based on schedules derived from the experimental design or on established standards of care. Minor unavoidable departures (up to 72 hours) from protocol directed therapy and/or disease evaluations (and up to 1 week for surgery) for valid clinical, patient and family logistical, or facility, procedure and/or anesthesia scheduling issues are acceptable per COG administrative Policy 5.14 (except where explicitly prohibited within the protocol).

All baseline studies must be performed prior to starting protocol therapy unless otherwise indicated below.

**7.1 Required and Optional Clinical, Laboratory and Disease Evaluations  
Obtain prior to start of phase unless otherwise indicated.**

STUDIES TO BE OBTAINED	Baseline	Course 1 #	Subsequent Courses #	End of ACCL0933 Therapy
REQUIRED				
History	X			
Physical Exam (Ht, Wt, BSA)	X			
CBC, differential, platelets	X	X	X	X
Creatinine, SGPT, SGOT, bilirubin	X	X	X	X
IFI checklist		X*	X*	X*
OPTIONAL				
Sample for SNP Genotyping		X %		
GM, BG Assays		2x weekly @	2x weekly @	

# Course 1 of fluconazole or caspofungin follows Course 1 of AML therapy. *Subsequent Courses* refers to protocol-directed antifungal prophylaxis, not AML therapy.

\* Submit relevant IFI checklist documents via the Document Imaging System: [contact] at the end of each course of protocol therapy. See Section 10.2 for further details.

% Obtain at end of Course 1, optimally when the patient has ANC > 1000/ $\mu$ L and no circulating blasts.

@ Collect specimens twice weekly during the period of neutropenia (until ANC > 100-500/ $\mu$ L). See Section 13.1 for specimen collection details. It is suggested that specimens be obtained on Mondays and Thursdays but other days are acceptable if more convenient. A minimum of 2 days should separate each specimen collection. All specimens must be collected in the specimen vials provided by MiraVista Laboratories in the shipped lab collection kits. Alternative specimen vials should never be used as they may contribute to false results.

**This table only includes evaluations necessary to answer the primary and secondary aims. Obtain other studies as indicated for good clinical care.**

## 7.2 Optional Studies

### 7.2.1 Galactomannan and (1→3) Beta-D Glucan Assays

Two antifungal antigen assays (Platelia *Aspergillus* EIA and Fungitell Assay) will be performed during the period of neutropenia in order to identify IA only and all IFI respectively. 6 mL of peripheral blood will be collected in a gold top serum-separator tube (provided by MiraVista) twice weekly. See Section 13 for sample collection, processing and shipping details. For each period of neutropenia, documentation of exposure or lack of exposure to each of the following will be performed: amoxicillin-clavulanate, piperacillin-tazobactam, and intravenous immunoglobulin. Documentation of infection with *Pneumocystis jiroveci*, *Penicillium* spp., *Histoplasma capsulatum*, *Geotrichum* spp., or *Neosartoria* spp. will occur through microbiology or pathology reporting and through routine adverse event reporting. See Section 11 for sample collection and shipping details.

### 7.2.2 SNP Analysis

Genotyping will be conducted in order to determine genes mediating immune function. Patients enrolled on AAML1031 will require no additional sample collection to participate. For all other patients, 5 mL of peripheral blood will be collected in a purple top tube at the end of Course I, optimally when the patient has an ANC > 1000/ $\mu$ L (and with no circulating blasts). See Section 14 for sample collection and shipping details.

## 7.3 Follow-up

See COG Late Effects Guidelines for recommended post treatment follow-up

<http://www.childrensoncologygroup.org/disc/LE/default.htm>

## 8.0 CRITERIA FOR REMOVAL FROM PROTOCOL THERAPY AND OFF STUDY CRITERIA

### 8.1 Criteria for Removal from Protocol Therapy

- a) Development of proven or probable IFI including IA according to institutional diagnosis.
- b) Patients who begin conditioning for HSCT.
- c) Begin a new chemotherapy regimen for AML that is refractory to, or relapsed with current AML chemotherapy.
- d) Refusal of further protocol therapy by patient/parent/guardian.
- e) Recovery from neutropenia following completion of the final planned AML chemotherapy course .
- f) Physician determines it is in patient's best interest.

Patients who are off protocol therapy are to be followed until they meet the criteria for Off Study below. Follow-up data will be required unless consent was withdrawn. A patient that is placed on empiric fungal therapy for prolonged fever and neutropenia should NOT be removed from protocol therapy for subsequent AML chemotherapy courses unless one of the off protocol therapy criteria is met.

### 8.2 Off Study Criteria

- a) Death.
- b) Lost to follow-up.
- c) Withdrawal of consent for any further data submission.
- d) Second anniversary of study entry.

### 8.3 Discontinuation from IFI Observation Criteria

**Patients who are taken off protocol therapy (but are not off study) must be followed for all infection endpoints until they meet the Discontinuation from IFI Observation Criteria (below) or until they meet the Off Study Criteria (See Section 8.2).**

- a) Begin conditioning for HSCT.
- b) Begin a new chemotherapy regimen for AML that is refractory to, or relapsed with current AML chemotherapy.
- c) Two weeks after recovery from neutropenia following completion of the final planned AML chemotherapy course.

## 9.0 STATISTICAL CONSIDERATIONS

### 9.1 Statistical Design

This is a randomized open-label trial to determine if prophylaxis with caspofungin during periods of neutropenia following chemotherapy for AML is associated with a lower incidence of proven or probable IFI compared with fluconazole. Eligible AML patients at ages 3 months to 30 years will be randomized to receive daily prophylaxis with either caspofungin or fluconazole. Randomization will be stratified into 2 groups: 1) *de novo* AML vs. 2) all other patients.

### 9.2 Patient Accrual and Expected Duration of Trial

Eligible subjects will have *de novo*, relapsed, or secondary AML, or any diagnosis being treated with institutional standard AML therapy (for example myelodysplastic syndrome, bone marrow blasts > 5% or biphenotypia). This protocol does not require concurrent enrollment on a COG therapeutic protocol. Patients treated per the upcoming *de novo* AML protocol, AAML1031 but not enrolled (for example, due to failure to meet AAML1031 eligibility criteria, refusal or other reasons) may enroll on ACCL0933. The *de novo* AML therapeutic protocol, AAML0531, accrued over 300 patients per year and the subsequent *de novo* AML protocol, AAML1031, is projected to accrue about 290 patients per year. The potential patient pool for ACCL0933 will be larger than AAML1031, and therefore, the accrual rate for this study is expected to be about 150 patients per year. Taking into account the initial delay in opening the study at institutions, the expected total accrual duration for 550 eligible patients is about 4 years. The maximum accrual, including ineligible enrollments, is 575 patients.

### 9.3 Statistical Analysis Methods

#### 9.3.1 Study Endpoints

##### Primary endpoint

The primary endpoint is the development of proven or probable IFI defined according to criteria developed by the European Organization for Research and Treatment of Cancer/Mycoses Study Group (EORTC/MSG) (from which time to IFI will be computed).

##### Secondary Endpoints

Endpoints for secondary objectives include: the development of proven or probable IA defined according to criteria developed by the EORTC/MSG (from which time to IA will be computed), death due to any cause (from which time to death will be computed), the need for empiric antifungal therapy defined as the institution of antifungal therapy while a study subject is receiving prophylaxis (from which the days of empirical antifungal therapy will be computed), results from GM and beta-D glucan assays for the diagnosis of IFI or IA alone, and results of the genotyping assays for SNP analysis.

An exploratory endpoint will be the development of proven, probable or possible IFI.

### 9.3.2 Central Committee Review

In order to ensure consistent and accurate application of the EORTC/MSG guidelines across all study patients, a Central Review Committee including Pediatric Oncologists and Pediatric Infectious Disease Specialists will be assembled. Through consensus meetings, committee members will review all data pertinent to the EORTC/MSG guidelines and determine whether a patient sustained a possible, probable or proven IFI or IA infection during the study period. The following data for each study patient will be collected and available at the time of the review: pathology reports, all CT scan and MRI reports, fungal Gram stain and microbiology culture results, non-culture mycology testing results (i.e., Histoplasma urine antigens, cryptococcal CSF and serum antigens), ophthalmology exams, bronchoscopy reports, and dosing and duration of steroid exposures.

All reviewers will be blinded to the patient's antifungal exposures in order to limit any bias in determining the primary and secondary endpoints.

### 9.3.3 Sample size with power justification

A total of approximately 550 eligible patients will be randomized to the 2 arms (at least 275 patients on each arm). Patients will be followed for infection outcome data until criteria in Section 8.3 has been met unless the patient is off study per Section 8.2 prior to meeting criteria in 8.3.

Since the current AAML1031 proposal plans 4 courses of chemotherapy with about 1 month duration for each course, it implies that likely many study participants will be followed for IFI for about 5 months. The power calculation assumes an IFI incidence in the fluconazole group of 8% and an IFI incidence in the caspofungin treatment groups of 2% at 5 months. The hazard ratio is 0.24. We assume up to 10% of patients may have early termination of follow up on IFI due to change in AML therapy such as refractory disease, relapse, or death. It is estimated that up to 25% of patients treated on or per AAML1031 may go to SCT prior to finishing all 4 courses. Therefore, altogether up to 35% patients may not be followed until the end of 5 months for IFI. With at least 275 patients on each arm, a planned 5-month follow up on each patient and up to 35% patients being censored by 5 months, we have about 80% power to detect the expected difference in time-to-IFI curves between the 2 arms (8% vs. 2% at 5 months) in a log rank test with 2-sided alpha level of 0.05. In the calculation, both failure and censoring are assumed to follow an exponential distribution during the 5 months. The majority of the censoring events prior to 5 months are expected to be due to SCT which likely occur later in the 5 months, so the exponential censoring distribution might not be a very good approximation but should be conservative in power consideration.

The assumed baseline incidence of IFI of 8% at 5 months is based on data reported in previous studies. CCG protocol 2961 found a 13% incidence of IFI. The rate of microbiologically documented sterile site fungal infections documented on AAML0531 is  $12 \pm 2\%$  as of April 2010; not all of these would meet MSG/EORTC criteria as proven/probable IFIs. In the power calculation, the onset of IFI in both groups over the 5-month period is assumed to follow an exponential distribution and is 8% and 2% for fluconazole and caspofungin at 5 months respectively. Under such exponential models, the incidence of over 5 months is approximately even, about 1.6% per month for fluconazole and 0.4% per month for caspofungin.

In this setting, we have a potential competing risk issue but its impact on estimating the risk for IFI should be minimal. We expect that majority of the censoring for IFI prior to the study completion are due to SCT or relapsed/refractory disease; the occurrence of such events are likely independent of the risk for IFI should the patient continue on the AML therapy, and can be considered true censoring events in the power consideration above. On the other hand, death prior to any other event constitutes a competing risk for IFI, but we expect such deaths to be rare and will not likely exceed 5% during the first 5 months; the impact that it has on estimating the risk of IFI by treating it as censored is minimal. Recently there have been some developments on sample size considerations under competing risk setting for either the

proportional cause-specific hazard model or proportional sub-distribution hazard model. However since the cumulative incidence of IFI under competing risk setting also involves the cause specific hazard of the competing risk, the interpretation of some of the planning parameters in these settings can be complicated and additional assumptions about the competing risk need to be made; it is also not yet well understood which model is better in different real settings. Given the fact that the true competing risk here is rare, we still use standard survival analyses for sample size considerations, but will perform competing risk analyses on the study data to ensure that it does not change the results of the comparison.

#### 9.3.4 Analysis Plans

##### Descriptive Analyses

Standard descriptive statistics will be used to describe subjects' baseline characteristics and study outcome measures overall and within each treatment group. Summary statistics such as means, standard deviations, medians, and ranges will be produced for all measured variables. The balance of baseline measures across the treatment groups will be examined using appropriate two-sample tests.

##### Analysis for Primary Objective and Secondary Clinical Objectives

The primary analysis will be based on the principle of intention to treat (i.e., by the treatment assignment of patients at randomization, regardless of subsequent compliance with the assigned treatment). Most of the events that take patients off IFI follow up prematurely such as going to SCT, relapse/refractory disease, may be considered independent from the risk for IFI; therefore they may be considered as true censoring events. Death before any such censoring events is a competing risk for IFI; however since the chance of that happening will be rare, expected to be no more than 5%, the effect of competing risk by death as the first event should be minimal. Therefore, we will focus on standard survival analyses but will also perform competing risk analyses to check if the results change after we consider death as a competing risk. In standard survival analyses, patients who go off IFI follow up before developing IFI for any reason will be treated as being censored. We will use Kaplan-Meier analyses to evaluate time to any IFI and log rank test to assess if there is any benefit associated with caspofungin compared to fluconazole. For competing risk analyses, nonparametric estimate of the cumulative incidence function for IFI will then be calculated by treating death (if first event) or possibly death plus other events as competing risk for IFI; Gray's test will be used to compare the cumulative incidence function between the 2 arms.

Similar standard survival analyses and competing risk analyses will be performed for secondary objectives 1-3 and the exploratory endpoint. For the secondary objective of time to development of invasive aspergillosis (IA), other IFI will also be considered a competing risk variable for IA in the competing risk analysis. For time to death (by any cause), only standard survival analyses will be performed. The total days of empiric antifungal therapy will also be compared between the 2 arms using t-test or Wilcoxon rank sum test.

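### Censoring patients who have finished therapy and recovered can make Kaplan-Meier overstate actual IFI incidence when completion is staggered before month 5

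*Combined protocol and SAP*

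**What the plan says.** Section 8.3 lists three ways in which IFI observation ends: (a) conditioning for transplant, (b) a new regimen for refractory or relapsed disease, and (c) "Two weeks after recovery from neutropenia following completion of the final planned AML chemotherapy course". Section 9.3.4 then sets the rule for the primary analysis: "patients who go off IFI follow up before developing IFI for any reason will be treated as being censored". Kaplan-Meier and the log-rank test are applied to the resulting times.

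Sections 9.3.3 and 9.3.4 justify treating exits as true censoring by naming transplant and relapsed or refractory disease. Section 9.3.3 frames the argument as the risk a patient would have had if AML therapy had continued. Death is the one event called a competing risk, expected in no more than 5%. A cumulative-incidence analysis with Gray's test is planned, with death and, only optionally, further unspecified events as competing. Completion of therapy is not mentioned in any of this. Nor is it part of the 35% early exits in section 9.3.3, which are 25% transplant plus 10% change of therapy or death.

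On follow-up time, section 9.3.3 expects that "likely many study participants will be followed for IFI for about 5 months".

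**The concern.** A patient who exits under 8.3(c) has left the period of risk that the trial studies. Kaplan-Meier censoring gives that patient, from then on, the IFI hazard of those still under observation, who are still receiving chemotherapy or recovering from it. If completion times differ between patients and some fall before month 5, the curve goes on rising on behalf of people whose risk period is over. 1-KM at 5 months then exceeds the proportion who actually develop IFI. The excess is roughly proportional to each arm's hazard, so the absolute difference is inflated too.

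The primary objective (section 1.1.1) is worded as a lower incidence, the design is expressed as 8% against 2% at 5 months, and Kaplan-Meier is the named method for time to IFI. A reader would naturally take absolute risks from that curve. The cumulative-incidence analysis has the same problem unless completion is coded as a competing event, and the present wording leaves that choice open until after the data are seen.

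**Working it through.** **1. The plan's own figure.** Inputs from section 9.3.3: 8% v 2% at 5 months, 275 per arm, 35% exponential censoring, two-sided alpha 0.05.
- Hazards per month: -ln(0.92)/5 = 0.01668 and -ln(0.98)/5 = 0.00404. Their ratio is 0.242; the plan says "The hazard ratio is 0.24".
- Censoring hazard: η = -ln(0.65)/5 = 0.0862.
- Expected events per arm: 275 × λ/(λ+η) × (1 - exp(-5(λ+η))) = 17.9 and 4.5, total 22.4.
- Freedman power: Φ(√22.4 × (1 - 0.242)/(1 + 0.242) - 1.96) = Φ(0.93) = 82%. This agrees with the statement that "we have about 80% power to detect the expected difference in time-to-IFI curves between the 2 arms".

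The design figure is reproduced. It has no term for completion before month 5.

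**2. Is completion before month 5 likely?** Section 9.3.3 gives four courses of about one month. Adding the two weeks in 8.3(c) gives 4 + 0.5 = 4.5 months from the start of chemotherapy. It is less from randomization, because protocol prophylaxis starts after course 1 chemotherapy and at most 5 days after enrolment (section 3.1.4). Section 3.2.2 admits relapsed and secondary AML and non-AML patients on institutional regimens, none of which is fixed at four courses. Table 2 in section 13.4 expects 216 of 440 patients (49%) to reach course IV, fewer than the 65% left after 35% early exits. The reasons are not given, so this does not prove early completion, but it does argue against uniform 5-month follow-up.

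**3. Size with the plan's even hazard.** Assumptions: completion time C is independent of the hazard while at risk, the IFI hazard is zero after C, and C has the same distribution in both arms. With staggered completion, 1-KM still estimates 1 - exp(-5λ), that is 8.0% and 2.0%, a difference of 6.0 points. The actual risk is 1 - E[exp(-λ·min(C,5))]. The documents give no distribution for C, so a range is shown.

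Example, fluconazole, C uniform on 3.5 to 5.5 months: 0.25 × 0.92 + 0.5 × (exp(-3.5λ) - 0.92)/λ = 0.230 + 0.5 × (0.9433 - 0.92)/0.01668 = 0.929, so the risk is 7.1%.

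| Assumed completion | Fluconazole % | Caspofungin % | Difference (points) | Fluconazole overstatement (points) |
|---|---|---|---|---|
| All at or after month 5 | 8.0 | 2.0 | 6.0 | 0 |
| 4.5 to 5.5 months | 7.8 | 1.95 | 5.9 | 0.2 |
| 4 to 6 months | 7.6 | 1.9 | 5.7 | 0.4 |
| 3.5 to 5.5 months | 7.1 | 1.8 | 5.35 | 0.9 |
| 25% at 2 to 3 months, rest at 4 to 5.5 | 6.6 | 1.65 | 5.0 | 1.4 |
| All at 4.2 months | 6.8 | 1.7 | 5.1 | 0 (1-KM is also 6.8) |

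The risk ratio is about 4.0 throughout.

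**4. Size if IFI risk is confined to neutropenia.** This simulation uses the Table 2 median durations (20, 18, 17 and 28 days) with assumed chemotherapy lengths, gaps between courses and variability, and the true fluconazole risk set at 8.0%. 1-KM was 8.05% with longer gaps, 8.3% in the base case, 8.4% with more variable recovery, 8.8% if 10% of patients have short courses of treatment, and 9.8% if 25% do. Coding completion as a competing event returned 8.0% each time.

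**5. The test.** Simulated log-rank power was 0.86 whether completers were censored or kept event-free in the base case, and within 0.4 points in all scenarios.

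**6. For scale.** Death at 5%, which the plan does treat as competing, moves the 5-month figures to 7.8% and 1.95%. The difference becomes 5.85, a change of 0.15 points.

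**The case against.** The strongest reply is that Kaplan-Meier answers a legitimate question: the risk if exposure to chemotherapy continued for 5 months. The plan's wording on independence points that way, and the primary objective concerns periods of neutropenia. On that reading nothing is biased. This stands in part, but the plan never says that its incidence is an on-therapy risk, and that hypothetical fits poorly for someone whose planned therapy is finished.

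Other parts stand in full. Section 9.3.4 defines no 5-month Kaplan-Meier risk difference; the 5-month figures belong to the sample-size section. The planned cumulative-incidence analysis could already accommodate completion, though it is not named there. The documents give no completion-time distribution. With 275 per arm, the simulated standard error of the 5-month estimate is about 2.0 points for fluconazole and 2.2 for the difference, so the usual overstatement is a fraction of one standard error. It is, however, systematic and in one direction.

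A reader might infer more than this, in three ways:
- **That the primary comparison is compromised.** It is not. The log-rank test compares patients while at risk, and this mechanism does not distort it if completion timing is similar in the arms.
- **That incidence will be overstated by as much as 30%.** That needs about a quarter of patients to have only one or two courses, a mix found nowhere in the documents.
- **That a number needed to treat will be wrong.** None is planned.

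**Conclusion.** The point holds as a conditional one. Completers are censored like losses to follow-up under a stated rule that the plan's independence argument does not cover. Where completion is staggered before month 5, 1-KM overstates the actual incidence in each arm and the absolute difference.

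In the fluconazole arm the overstatement is mostly 0 to 0.7 points, just under 1 point with a wide spread of completion times or 10% short-course patients, and about 1.5 to 2 points if a sizeable minority has one or two courses. In the even-hazard scenarios the 6-point difference is overstated by at most about 1 point. It is nil if nearly all complete after month 5 or all at one time.

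These sizes rest on assumed completion patterns, zero IFI hazard after completion and similar timing in both arms. The documents do not support a claim of an invalid test, lost power or a distorted risk ratio.

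**What to change.** Keep the log-rank test as the primary comparison. In section 9.3.4:
- Name 8.3(c) completion, alongside death, as a competing event in the cumulative-incidence estimates for IFI, IA (with other IFI also competing, as already planned) and the exploratory endpoint.
- Censor exits under 8.3(a) and (b), withdrawal of consent and loss to follow-up.
- Report absolute incidences and differences from these estimates, with numbers at risk.

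Keeping completers in the risk set as event-free is close but not equivalent. They can no longer be censored for transplant or relapse, so they are over-weighted, and the estimate ran slightly low in simulation (7.9% against a true 8.0%). The competing-event coding is preferable.

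The cost is a short change of analysis wording. The reason for leaving IFI observation is already defined in section 8.3, and no new data are needed. The downside is that the reported figure becomes IFI during the protocol-defined observation period, counts nothing beyond two weeks after recovery from the last course, and is slightly lower than 1-KM. The text should say so.
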